2.2 RATIONALE

We hypothesize that IL-1Ra administered intra-articularly during the early phase of acute ACL injury will provide symptomatic pain relief and decrease synovial fluid inflammatory and cartilage degradation markers. ACL injury produces high levels of inflammatory mediators, including as IL-1, which mediate knee pain, perpetuate synovitis, and decrease functional recovery post injury and post-surgically. We have designed a clinical trial that specifically tests the ability of IL-1ra to alleviate pain following acute ACL injury and potentially changes patient reported outcomes at 2 years.

A total of 1 mL (150 mg) will be injected intra-articularly after synovial fluid aspiration 'to dryness' once at study entry 1-28 days after injury depending on time of presentation).

Rational for including pediatric population

The specific reason for enrolling the age group of children aged 14-18 is that these children have a musculoskeletal physiology like adults.

- Their major growth plates are closed.
- These patients may be treated surgically like adult patients with exactly the same surgical preparation, technique and rehabilitation as adults.
- Children, particularly girls, between the ages of 14 and 18 have the highest statistical risk in any population of tearing their Anterior Cruciate Ligament. ^{25,45}
- Children in this age group are particularly vulnerable to the later development of osteoarthritis. Lohmander et al showed that young female soccer players in this age group developed symptomatic knee Osteoarthritis secondary to the ACL injury within 12 years of the injury.²⁴ One could therefore argue that particularly children between completed puberty and 18 years of age have to be the patients requiring most of our concern regarding development of OA.
- *Furman et al.* showed that early post-injury administration of IL-1Ra did not alter bone morphology or fracture healing after intra-articular fracture but significantly reduced cartilage degradation and inflammation.⁽⁴⁶⁾
- The value of intraarticular IL-1 blockade when given immediately after intraarticular injury has been demonstrated repeatedly. In a recent publication of *Genemaras et al.* the early administration of IL-1Ra could be shown to significantly down-regulate proinflammatory Il1-β, TNF-α) and chondrodegredatory markers (MMP-3,ADAMTS-4,ADAMTS-5) immediately after non-destructive chondral impact injury to porcine articular cartilage⁽⁴⁵⁾.
- *Chevalier et al.* showed in 2005 that intra-articular injection of anakinra in patients with knee OA is safe ⁽⁴⁷⁾. It is important to realize that patients who have suffered an ACL injury are a substantial risk for chronic inflammatory changes leading to OA and, in fact, display these changes as early as 4 weeks after injury lasting for up to 5 years after ACL injury. ^(48,49)
- A study performed by Brown et al. enrolled 8 patients with arthrofibrosis who were treated with intra-articular administration of 150mg of anakinra. Five of the eight enrolled patients were under the age of 24, 3 under the age of 21, and one patient aged 15. None of these patients have shown any adverse events and all of them improved in their clinical outcomes. In addition the same group completed a study enrolling young patients (mean age 22±3) who suffered ACL injuries. This trial did also not show any

significant adverse events regarding safety of the drug administration. In contrary, they show improved post-injury pain scores.⁵²

In summary: We would like to argue that skeletally mature adolescents of ages 14-18 are musculoskeletally no different than their 19 year old and older counterparts and therefore deserve the same potential benefit that early treatment with IL-1Ra may offer older patients. We find of no data to indicate that intra-articular use of IL-1Ra would have a different effect in the 14-18 year old over the 19-40 year old. There is no in-vitro or in-vivo data indicating a detrimental effect of Il-1Ra to articular cartilage or the knee joint as a whole in the dosages we are intending to use. We believe that the potential benefits of this trial for this patient population outweighs by far the uncertainty of unknown risks that may be associated specifically with being 14-18 year old.

The Federal Drug Administration has approved daily subcutaneous injections (100 mg) to patients with rheumatoid arthritis. Our goal is to sustain therapeutic levels of IL-1Ra in the joint during the early phase of acute joint injury. We hypothesize that the post injury intra-articular administration of 150 mg IL-1Ra (Kineret®) will be well tolerated.

By slowing the initial inflammatory process after injury and preventing the significant quadriceps muscle shutdown early, we aim to work towards this goal in this trial. We therefore conclude that given the limited risk of local side effects and the potential large benefit that this study would provide to the scientific community and its potential to significantly improve and alter patient care of young individuals suffering ACL injuries it is not reasonable to withhold pediatric patients aged 14-18 from this important trial.

2.3 POTENTIAL RISKS AND BENEFITS

2.3.1 KNOWN POTENTIAL RISKS

Safety Precautions: Participants will be followed at regular intervals by their study doctor. During each visit participants will be evaluated for adverse events according to GCP guidelines and reported accordingly to IRB and FDA regulations.

Risks associated with Kineret®:

Reproductive Risks: It is not known whether receiving Kineret® is harmful to an unborn child. Pregnancy after administration of Kineret® may involve risks to the mother, and her embryo or fetus. Therefore, females who are capable of reproducing, must use effective contraceptive methods. These methods must be used from the time of screening until Visit 2 during which any remaining medication will be washed out of the joint during the surgery. If the participant does not elect to have surgery (visit 2) contraception methods will be documented until the end of the study. Examples of effective birth control are: hormonal contraceptives (the pill, implant, transdermal patch, or injection), barrier methods (condom with spermicide, diaphragm with spermicide), IUD, or a male partner had a vasectomy.

Lactating women: It is not known whether this drug or its metabolites are excreted in human milk. Because many drugs are excreted in human milk, caution should be exercised when Kineret® is administered to a nursing woman.

Limitations, potential problems, and alternatives: This study will allow for safety and efficacy assessment in patients with acute effusive knee injury.

- Dose: Based on our work and the work of others, we believe 150 mg dosage is appropriate. The goal of the study is to sustain levels of IL-1Ra long enough and a high enough concentrations during the critical, early time period to be effective. For this reason, we have increased our dosage from a single injection (carried out in the preliminary study) to two injections.
- Patient attrition: Close and regular communication, particularly in the intensive first few months, will be provided to all subject participants. Patients will be fully informed of the time commitments and need for a total of three arthrocenteses in order to recruit study subjects willing to participate in the full study. Because arthrocentesis alone can be expected to benefit subjects, education regarding direct and indirect benefits of all aspects of the trial will be provided. Subjects will also receive appropriate compensation for the time and travel.

2.3.2 KNOWN POTENTIAL BENEFITS

IL-1Ra, while potent, has had mixed results in the treatment of established OA, possibly due to its short half-life in vivo. In this trial, we expect that an early intervention with IL-1Ra will effectively block the deleterious cascade of joint degradation events after joint injury. We expect a significant effect of IL-1Ra on post-injury pain and concomitantly an increased improvement in early function.

3 OBJECTIVES AND PURPOSE

Primary Objective: To assess the efficacy of using IL-1ra and knee arthrocentesis to alleviate inflammation related knee pain and improve patient-reported outcomes (PRO) following ACL rupture.

Secondary Objectives:

1. To determine if intra-articular IL-1ra therapy improves levels of a panel of inflammatory, meniscus and cartilage metabolism, and oxidative stress biomarkers as measured in synovial fluid, serum and urine from patients immediately after ACL injury (baseline, 2 weeks after injury and at 1 and 2 years after surgery).

2. To assess if MRI T1rho changes correlate with synovial biomarker levels and show predictive value for the overall subject patient outcome at 2 years

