- To assume responsibility for the proper conduct of the study and not to deviate from the procedures described in the protocol.
- I am thoroughly familiar with the investigational product(s) as described in the protocol, Investigator's Brochure and any other relevant information sources provided to me.
- I am aware of and will conduct the study in compliance with the protocol, ICH GCP guidelines and all applicable regulatory requirements.
- I agree to permit monitoring and auditing of the study by the Sponsor and its designates, and inspection by appropriate regulatory authority (ies).
- I agree to ensure that all persons assisting with the conduct of the study are properly qualified for their function.

Investigator Name & Signature:

Principal Investigator: [name] Print/Type Name

Signed: _____

Signature

[figure not shown]
Date:

PROTOCOL SUMMARY

Title:	A Prospective, Multicenter, Randomized, Triple-Blinded, Placebo-
	Controlled study of IL-1RA Treatment in Patients with Acute ACL
	Tear and Painful Effusions
Précis: Objectives:	This study aims to establish efficacy and timing of administration, to reduce post-injury pain, decrease inflammatory biomarkers in ACL injured patients undergoing ACL reconstruction and correlate function, patient reported outcomes and MRI findings at 1 years after ACL injury. The study population will include 40 subjects, ages 14-40 who will be randomized into 2 groups (20 subjects per group). 1. Test the efficacy of a treatment protocol using IL-1ra and knee arthrocentesis to alleviate inflammation related knee pain and improve patient-reported outcomes (PRO) following ACL rupture. 2. Determine if intra-articular IL-1ra therapy improves levels of a panel of inflammatory, meniscus and cartilage metabolism, and oxidative stress biomarkers as measured in synovial fluid, serum and urine from patients immediately after ACL injury (baseline, 2 weeks
	after injury and at 1 and 2 years after surgery).3. Answer the question if MRI T1rho changes correlate with synovial biomarker levels and show predictive value for the overall subject patient outcome at 2 years.
Endpoint	Primary endpoint : Change in Patient reported outcomes as measured by KOOS- Symptoms
	Secondary endpoints: KOOS QOL, KOOS-pain, KOOS-Sports/Rec, Biomarker levels in synovial fluid, serum and urine at time of surgery MRI T1rho changes at 2 years
	Study Stopping Criteria

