4.2 STUDY ENDPOINTS

4.2.1 PRIMARY ENDPOINT

Patient reported outcomes as measured by KOOS-Symptoms

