7 STUDY PROCEDURES AND SCHEDULE

7.1 STUDY PROCEDURES/EVALUATIONS

7.1.1 STUDY RELATED

Demographic information: Demographic data to be collected at Visit 1 will include height, weight, date of birth, age, gender and race.

Medical and Medication History A detailed past medical history and a list of current medication, to include prescription and over-the-counter medications, will be collected at Visit 1. Assessment of eligibility should include a review of permitted and prohibited medications. Both the medical and medication history will be reviewed with the subject throughout the study for any changes in baseline history.

Physical examination including vital signs, height, weight, BMI. All subjects must have a clinical exam that is consistent with an ACL tear at Visit 1. All subjects will have range of motion (ROM) collected at all visits.

Knee Aspiration: All subjects undergo knee aspiration to dryness at initial encounter Visit 1 (1-28 days after ACL injury), Visit 2 (the time of surgery) and again at Visit 3 (4-14 days post-op). Should a subject be enrolled into the study and choose not to undergo ACL reconstruction, subject will receive treatment according to this protocol but, aspiration at time of surgery will be omitted.

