Assessment of Pain and Function –Subject Reported Outcomes – The study will use the standardized subject self-report Knee Injury and Osteoarthritis Outcome Score (KOOS) instrument to assess pain and function in response to the intervention for acute ACL injury. The KOOS is a 100 item instrument that consists of 5 subscales (pain, other symptoms, function in daily living, function in sport and recreation, and knee-related quality of life). The 5 separate subscales provide a complete picture of patients' perceptions of their knee injury and consequences to their daily activities, etc.. KOOS includes the WOMAC osteoarthritis index, which allows for potential comparison with other earlier studies. The KOOS has high test-retest reproducibility (ICC > 0.75). The KOOS subscales for function in sport and recreation and knee-related quality of life have been shown to be the most sensitive subscales pre-operatively and change the most post-operatively (27). The study will supplement the KOOS with self-reported function score assessments from the International Knee Documentation Committee (IKDC) form for evaluation of knee ligament injuries (28) as well as the. Veterans Rand 12-Item (VR-12) health survey and the Patient Acceptable Symptoms State (PASS) question. The questionnaires will be assessed either via an internet based collection software that allows secure data collection

[figure not shown]
through a password coded entry portal or during routine clinical visits using an IPad or paper forms. Paper forms may be used during routine clinical visits or directly mailed to patients.

Specific Pain assessments - Pain coping strategies are important in understanding improvements in pain and psychological disability [46-48]. This study will use a simple Likert pain scale as a pain assessment tools (Figure 3). Pain catastrophizing has been identified as one of the strongest predictors of pain and has been defined as "an individual's tendency to focus on and exaggerate the threat value of painful stimuli and negatively evaluate one's own ability to deal with pain." [49] Not only do individuals who catastrophize, experience more experimental pain (29-31) but also, catastrophizing has been shown to account for 7% to 31% of the variance in pain ratings in varied populations of patients having persistent pain.

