10 STATISTICAL CONSIDERATIONS

10.1 STATISTICAL AND ANALYTICAL PLANS

10.1.1 GENERAL APPROACH

Sample Size and Power Analysis - The primary outcome aim of the study is to determine if treatment with the study medication results in greater improvements in patient-reported outcomes one year following surgery. We will use the validated Knee Osteoarthritis and injury Outcome Score (KOOS),[27] which is a self-administered, knee-specific instrument that evaluates the course of knee injury and treatment outcomes. To reduce the risk of an underpowered RCT, an a priori sample size estimation was calculated from data collected from recent studies of ACL-injured and -reconstructed patients.[28-32] The previously published oneyear KOOS Quality of Life Scores are 60.2 ± 24.2 [31] and the minimal detectable change of this instrument is 7.2 [32]. Assuming that the standard deviation of the change scores between the day of surgery and one year postoperative visits will be 20% of the standard deviation of the standard deviation of the one-year KOOS Quality of Life Scores ($.2 \times 24.2 = 4.8$), a sample size of 16 patients per group (32total) would be at least 80% powered to detect a difference of 7.2 points between the treatment group and the control group (One-way ANOVA model with alpha = 0.05, Effect size = 7.2/4.8 = 1.5, G*Power 3.0.10). This sample size would adequately power the study for the primary outcome variable, but would also adequately power the study for the second aim of the study. The second aim of the study is to compare chondrodegenerative biomarkers between groups at the 1 year follow up. We have previously observed large effect sizes between groups in preliminary studies (ES = 1.34), and a sample size of 32 patients (16 per group) would be at least 80% powered to detect effect sizes of this magnitude. However, to protect against an underpowered study due to patient attrition, we will monitor compliance and potentially enroll up to 20 patients per group in order to adjust for attrition. Patient costs will not occur until sample or MRI analysis.

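### The primary endpoint (KOOS-Symptoms) tests only the patient-reported-outcome part of the primary objective; its pain and arthrocentesis parts have no primary test, and the power statement rests on a different, secondary subscale

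*Combined protocol and SAP*

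**What the plan says.** Section 3 gives the primary objective in two parts. It begins "To assess the efficacy of using IL-1ra and knee arthrocentesis to alleviate inflammation related knee pain" and continues "and improve patient-reported outcomes (PRO) following ACL rupture". The rationale in section 2.2 stresses the first part: "We have designed a clinical trial that specifically tests the ability of IL-1ra to alleviate pain following acute ACL injury".

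The primary endpoint in section 4.2.1 is "Patient reported outcomes as measured by KOOS-Symptoms". The Protocol Summary has "Change in Patient reported outcomes as measured by KOOS- Symptoms". Neither gives a time point. Section 4.2.2 lists KOOS QOL, KOOS-pain and KOOS-Sports/Rec as secondary. Section 7.1.1 describes the KOOS as having "5 subscales (pain, other symptoms, function in daily living, function in sport and recreation, and knee-related quality of life", so pain and other symptoms are separate scores.

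The sample-size paragraph in section 10.1.1 uses another subscale: "The previously published oneyear KOOS Quality of Life Scores are 60.2", with an SD of 24.2. It takes 7.2 points as the difference to detect, concludes that 16 per group suffices, and states that this is adequate power for the primary outcome.

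On aspiration, section 7.1.1 says "All subjects undergo knee aspiration to dryness at initial encounter Visit 1". Under sections 4.1 and 6.1.5 the two groups differ only in receiving IL-1ra or saline.

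**The concern.** The objective, the endpoint and the power statement should describe the same comparison, and here they do not. Pain comes first in the primary objective, but no primary test is attached to it. A positive KOOS-Symptoms result would not show pain relief, and a real effect on pain could appear only in a secondary analysis. Section 10.1.3 specifies no analysis for secondary endpoints, and the analysis paragraph in 10.1.1 speaks of change in KOOS without naming a subscale.

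The power statement matters separately. A reader will take it as assurance about KOOS-Symptoms, although its inputs describe a secondary endpoint.

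Finally, the objective speaks of the efficacy of IL-1ra and arthrocentesis together. Since both arms are aspirated, the randomised comparison gives no evidence on arthrocentesis, alone or as part of the combination.

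**Working it through.** **Matching the parts of the objective to a test**

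- Knee pain: KOOS-pain (secondary, section 4.2.2) and a Likert pain scale (collected under section 7.3.1). No primary test.
- Patient-reported outcomes: KOOS-Symptoms is one of these, so the primary test applies.
- Arthrocentesis: given in both arms at Visit 1, so it cancels out of the comparison.

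What the primary test estimates is the effect on KOOS-Symptoms of IL-1ra versus saline, both after aspiration.

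**Inputs to the sample size (all from section 10.1.1)**

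KOOS Quality of Life SD at one year 24.2; SD of change taken as 20% of this, 0.2 × 24.2 = 4.84 (rounded to 4.8); difference 7.2; effect size d = 7.2/4.8 = 1.5; alpha 0.05; one-way ANOVA, which with two groups equals a two-sided t test; at least 80% power; 16 per group, with up to 20 to cover attrition.

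**The plan's own figure**

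Normal approximation: n per arm = 2(1.96 + 0.84)² / d² = 15.7 / 2.25 = 6.98, so 7. The exact t test, or the ANOVA with f = d/2 = 0.75, gives 9 per arm. At 16 per arm the noncentrality is 1.5 × √(16/2) = 4.24 and exact power is 98.4%. The claim of at least 80% is therefore true for these inputs, although they do not lead to 16. That difference is a separate matter from this point.

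**What 16 to 20 per arm requires of KOOS-Symptoms**

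The smallest d with 80% power (exact t, two-sided 0.05) is 1.02 at 16 per arm and 0.91 at 20. The largest change SD compatible with 7.2 points is then:

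- 16 per arm: 7.2 / 1.024 = 7.03
- 20 per arm: 7.2 / 0.909 = 7.92

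The documents give no KOOS-Symptoms SD to compare with these limits. The next table assumes a 7.2-point difference on KOOS-Symptoms and a range of change SDs. Only 4.8 and 24.2 appear in the plan, and both describe Quality of Life (the first as an assumed change SD, the second as an SD of scores).

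| Assumed change SD | Power at 16 per arm | n per arm for 80% power (exact t) |
|---|---|---|
| 4.8 | 98.4% | 9 |
| 10 | 50.4% | 32 |
| 15 | 26.0% | 70 |
| 20 | 16.7% | 123 |
| 24.2 | 12.9% | 179 |

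The answer depends almost entirely on a figure that the plan does not supply for its primary endpoint.

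**The case against.** The strongest reply is that the objective does not stop at pain. It also covers patient-reported outcomes, and KOOS-Symptoms is one. The rationale likewise goes on to outcomes at 2 years, and section 10.1.1 states the primary aim purely in terms of patient-reported outcomes one year after surgery. This stands. A reader might infer that the primary result cannot answer the objective at all; the documents do not support that, because the second part is addressed.

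A reader might also count three conflicting subscales. The objective names pain as a concept and no KOOS subscale. The conflict between subscales is between Symptoms (endpoint) and Quality of Life (sample size).

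Aspirating both arms might be read as a design fault. It is a sound way to isolate the drug, and the hypothesis, design description and power section all concern IL-1ra. The difficulty lies only in how the objective is worded.

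The Quality of Life inputs might suggest that the trial is underpowered for KOOS-Symptoms. Without an SD for that subscale this cannot be said, only that the power claim has no support. Nor do these inputs stop KOOS-Symptoms from addressing its part of the objective.

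Lastly, one might conclude that KOOS-Pain must become primary. That is a trade-off, not a correction. The remark in section 7.1.1 on the most sensitive subscales names Sport/Recreation and Quality of Life, so it favours neither Pain nor Symptoms. Pain is not neglected either: the KOOS and the Likert scale are collected at Visits 1, 2, 4, 5 and 6.

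**Conclusion.** The point holds in three limited parts. First, the pain part of the primary objective has no primary test; pain is assessed only through secondary or supporting measures. Second, the statement that the primary outcome is adequately powered is unsupported, because its inputs belong to a secondary subscale. It would hold for a 7.2-point difference only if the KOOS-Symptoms change SD were about 7.0 or less at 16 per arm, or about 7.9 or less at 20. These limits assume a two-sided alpha of 0.05, a two-sample comparison of change scores, and that 7.2 points, quoted in a sentence about Quality of Life, is also the relevant difference for Symptoms. Third, the trial cannot credit any effect to arthrocentesis or to the combination. None of this invalidates the randomised comparison of IL-1ra with saline on KOOS-Symptoms.

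**What to change.** 1. Use one named subscale and one time point for the primary objective, the primary endpoint and the sample size, in the Protocol Summary and sections 3, 4.2.1 and 10.1.1.
2. If KOOS-Symptoms stays primary, reword the objective so that pain is a secondary aim.
3. Restate the power, or the detectable difference, at the planned 16 to 20 per arm with a sourced SD for change in KOOS-Symptoms. If none can be found, withdraw the statement that the primary outcome is adequately powered.
4. Word the objective as IL-1ra versus placebo, both after arthrocentesis.

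The cost is rewording and one calculation; the KOOS is already collected, so no visit or procedure is added. The downside is that the stated power may become less favourable, and that no pain claim can then rest on the primary test.

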7.3 STUDY SCHEDULE

7.3.1 SCREENING/ENROLLMENT

Visit 1 Screening 1-28 days following injury)

- Obtain informed consent and assent, if necessary, of potential subjects
- Review medical history to determine eligibility based on inclusion/exclusion criteria.
- Review medication history to determine eligibility based on inclusion/exclusion criteria.
- Perform medical examinations and collect vital signs as needed to determine eligibility based on inclusion/exclusion criteria. All subjects must have a clinical exam that is consistent with an ACL tear.
- Collection of urine and blood for laboratory testing. Women of child bearing potential will be given a urine pregnancy test. Test must be negative in order to enroll into the study.
- Subjects will have the following assessments: range of motion, knee instability (Lachman's test) and standardized MTP-2 weight bearing x-rays.
- Standard questionnaires including the KOOS, IKDC, VR-12 and a Likert pain scale.
- Research knee MRI

Following the review of above assessment results and a review of inclusion/eclusion criteria, subjects will be randomized into 1 of 3 treatment groups. Following randomizing, subjects will undergo a knee aspiration and will receive their first dose study medication.

Visit 2 (day of surgery or 4-6 weeks post injury)

- Knee aspiration (in the operating room under anesthesia)
- Patient reported outcomes (PROs) administered prior to surgery
- KOOS, IKDC, VR-12 and a Likert pain scale administered prior to surgery
- Biomarkers (urine and blood) pre-operatively
- Review for AE's and SAE's
- ROM will be performed prior to surgery

Visit 3 (4-14 days After Visit 2)

- Knee aspiration (if clinically indicated)
- Biomarkers (urine and blood)
- Review for AE's and SAE's
- ROM will be performed

Visit 4 (6 month After Visit 2+/- 2 weeks)

- Patient reported outcomes (PROs) administered
- KOOS, IKDC, VR-12 and a Likert pain scale administered
- Review for AE's and SAE's

• ROM will be performed

Visit 5 (12 monthsAfter Visit 2+/- 2 weeks)

- ÀRI
- Patient reported outcomes (PROs) administered
- KOOS, IKDC, VR-12 and a Likert pain scale administered
- Biomarkers (serum and urine only)
- Review for AE's and SAE's
- ROM will be performed

Visit 6 (24 month After Visit 2+/- 2 weeks)

- MRI
- Patient reported outcomes (PROs) administered
- KOOS, IKDC, VR-12 and a Likert pain scale administered
- Biomarkers (serum and urine only)
- Review for ÀE's and SAE's
- ROM will be performed

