The power calculations include several caveats. First, for purposes of power calculation, we did not assume a full repeated measures analysis, but instead analyzed at a single time point (oneyear follow-up). Second, we note that in trials such as this, the power of a non-parametric analysis is never much lower than its parametric analog (the "asymptotic relative efficiency" of the Wilcoxon test is at least 0.95), leading us to conclude that our parametrically based power calculations should apply with equal force to a non-parametric analysis.

Statistical analyses - Results from a sample of this size may not be normally distributed. Therefore, non-parametric statistical measures may be used. Primary outcome measures evaluating for change in KOOS will be assessed at multiple points and will be analyzed for change between groups using Friedman two-way ANOVA for repeated measures. Synovial fluid analyses comparing the three groups at five time points will be analyzed using the Wilcoxon Signed Rank Sum Test with Hochberg corrections for multiple time points. Alternatively, if results are normally distributed or can be transformed (e.g., by log transformation) to meet the criteria for normality for parametric analysis, then repeated measures ANOVA will be utilized comparing treatment groups. P-values of less than or equal to 0.05 will be considered statistically significant.

Predicted Results: IL-1ra, while potent, has had mixed results in the treatment of established OA, possibly due to it's short half-life in vivo. In this trial, we expect that an early intervention with IL-1ra will effectively block the deleterious cascade of joint degradation events after joint injury. We expect a significant effect of IL-1ra on post-injury pain and concomitantly an increase in patient-reported outcomes due to the improved early function

Minimization of bias: Due to the randomized study design and the blinding of the investigator and patient to the drug used, we hope to eliminate any investigator or subject bias. Using broad and previously established enrollment criteria we hope to reduce selection bias to a minimum while protecting potentially vulnerable individuals through the exclusion criteria. Procedural bias and measurement bias will be reduced by the multicenter design and the blinded data analysis.

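### The synovial-fluid times in secondary objective 1 and the five-time-point synovial analysis do not match a schedule that aspirates the knee at three visits at most

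*Combined protocol and SAP*

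**What the plan says.** Four parts of the plan name times for the biomarkers.

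- **Objective.** Section 3, secondary objective 1 (repeated in the Protocol Summary) concerns "oxidative stress biomarkers as measured in synovial fluid, serum and urine from patients immediately after ACL injury". The times it lists are "baseline, 2 weeks after injury and at 1 and 2 years after surgery".
- **Endpoint.** Section 4.2.2 names biomarker levels in the three fluids at the time of surgery.
- **Power.** Section 10.1.1 describes the second aim as a comparison of chondrodegenerative biomarkers at 1 year, with effect size 1.34 and 16 patients per group.
- **Analysis.** Section 10.1.1 states: "Synovial fluid analyses comparing the three groups at five time points will be analyzed using the Wilcoxon Signed Rank Sum Test". A Hochberg adjustment is to cover the several times. Section 10.1.3, on analysis of secondary endpoints, is marked not applicable, so this sentence is the only biomarker analysis in the plan.

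The sampling is set elsewhere.

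- Section 7.1.1: "All subjects undergo knee aspiration to dryness at initial encounter Visit 1 (1-28 days after ACL injury), Visit 2 (the time of surgery". The same sentence adds a third aspiration for all subjects, at Visit 3. The Visit 2 aspiration is omitted without surgery.
- Section 7.3.1 makes the Visit 3 aspiration depend on clinical indication. Note h of the table in 7.3.2 limits it to operated patients with fluid in the knee.
- At Visits 5 and 6 (12 and 24 months), section 7.3.1 lists "Biomarkers (serum and urine only". Note d of the table agrees.
- Section 2.3.1 says patients will be told of the "need for a total of three arthrocenteses".
- Timing is "Visit 2 (day of surgery or 4-6 weeks post injury" for Visit 2, days 1 to 28 after injury for Visit 1, and 4 to 14 days after Visit 2 for Visit 3.

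**The concern.** An analysis at five synovial time points needs five synovial samples per patient, and the schedule cannot supply them. The objective's late times also coincide with the two visits at which no joint fluid is drawn. Meanwhile the objective's list omits the surgery sample, which is the one post-injection aspirate common to the operated patients and the one the endpoint names.

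Three things are at stake.

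1. With 16 to 20 patients per group and different times in the objective, endpoint, power statement and analysis, the fluid and time that carry the biomarker conclusion could be chosen after the data are seen.
2. The Hochberg family has no defined size, so the threshold that a result must meet is unknown.
3. Section 7.2.1 describes nearly every marker (the cytokines, GAG, CTX-II, NTX-I, xanthine oxidase) as a synovial-fluid measurement, and COMP is the one discussed mainly as a serum marker. The 1-year comparison used for power falls where no synovial fluid exists.

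**Working it through.** **Step 1. Count scheduled samples by fluid** (sections 7.1.1, 7.3.1 and 7.3.2).

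| Visit | Synovial fluid | Serum/blood and urine |
|---|---|---|
| 1 (day 1-28) | yes, before the injection | yes |
| 2 (surgery, or 4-6 weeks) | only if operated | yes |
| 3 (4-14 days after Visit 2) | operated, fluid present (note h) | yes |
| 4 (6 months) | no | no |
| 5 (12 months) | no | yes |
| 6 (24 months) | no | yes |
| **Total** | **3 at most** | **5** |

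Visit 1 is before dosing because section 7.2.1 attaches the drug syringe after the aspiration.

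**Step 2. Compare with the analysis sentence.** The stated number of synovial time points is 5. The schedule gives 3 at most, 2 for an operated patient without fluid at Visit 3, and 1 for a patient who is not operated on. At most 3 − 1 = 2 follow the injection. The stated figure does not reproduce for synovial fluid. It does equal the serum and urine count, of which 5 − 1 = 4 are post-dose.

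**Step 3. Compare with the objective's four times.**

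| Time in objective 1 | Synovial fluid | Serum and urine |
|---|---|---|
| Baseline | Visit 1 | Visit 1 |
| 2 weeks after injury | no fixed visit | no fixed visit |
| 1 year | none | Visit 5 |
| 2 years | none | Visit 6 |

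For a patient enrolled on days 15 to 28, the 2-week point has passed before baseline. For a patient without surgery, Visit 2 falls on days 28 to 42 and Visit 3 on days 32 to 56 (28 + 4 to 42 + 14), so neither reaches week 2.

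**Step 4. Size of the Hochberg family.** With m times, the smallest p-value must meet 0.05/m when no larger one has passed its own step.

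- m = 5: 0.05/5 = 0.01
- m = 4: 0.05/4 = 0.0125
- m = 2: 0.05/2 = 0.025
- m = 1: 0.05, with nothing to correct

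**Step 5. The second-aim power figure.** Inputs are effect size 1.34, n = 16 per group and two-sided alpha 0.05. The normal approximation is Φ(1.34 × √(16/2) − 1.96) = Φ(3.79 − 1.96) = Φ(1.83) = 0.966. A two-sample t-test gives 0.956, and 0.842 at alpha 0.01. The claim of at least 80% reproduces, even at the strictest five-time threshold. The difficulty is the fluid: at 1 year the comparison exists only in serum and urine. The plan does not say from which marker or fluid the 1.34 came.

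**Step 6. The test and the groups.** The signed-rank test is for paired or one-sample data, so it tests change within patients and does not compare groups. The sentence speaks of three groups, while section 4.1 defines two.

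**The case against.** The strongest reply is that the objective puts three fluids and four times in one sentence without assigning every fluid to every time. Read with the schedule, 1 and 2 years would be serum and urine times, and only the 2-week time would lack a visit. The surgery sample is also not lost, since section 4.2.2 makes it an endpoint and Visit 2 collects it.

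Much of this stands, and it rules out several stronger readings.

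- A reader might infer that objective 1 as a whole cannot be carried out. The documents do not support that: serum and urine are scheduled at three of its four times.
- A reader might infer that three of four promised synovial samples are never taken. That requires the every-fluid-at-every-time reading, which the sentence allows but does not state.
- A reader might infer that no sample can fall at 2 weeks. One can, by chance. Visit 1 may fall near day 14, and in the group's earlier trial of the same design time to surgery ranged from 10 to 51 (section 2.1, Table 1; the unit is not printed and is taken to be days). No visit secures such a sample.
- A reader might take the schedule as right and the objective as wrong. The documents do not say which reflects the intent.

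The reply does not rescue the five synovial time points, and it does not provide a 2-week visit in any fluid.

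**Conclusion.** The mismatch holds for the synovial part of objective 1 and for the synovial analysis. Five synovial times are stated and at most three are scheduled, one before dosing and two conditional. None is at 1 or 2 years, and no fluid has a visit fixed at 2 weeks. The serum and urine part is feasible as regards sampling, apart from the 2-week time. The surgery-time endpoint and the 1-year power statement do not agree with each other or with the analysis sentence.

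This is an inconsistency in secondary material and leaves the primary KOOS endpoint untouched. It rests on the schedule in section 7.3 being what is carried out. If section 7.1.1 governs Visit 3, the maximum of three is unchanged, but more patients reach it. It would be an inference, not documented, that the five-time, three-group sentence came from another design or from the serum and urine count.

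**What to change.** Restate objective 1 (and its copy in the summary), the section 4.2.2 endpoint, the second-aim power statement and the analysis sentence by fluid and visit, naming the markers assayed in each fluid.

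- **Synovial fluid.** Make the between-group comparison at Visit 2, the time the endpoint names, with the Visit 1 value as baseline. Report Visit 3 as supportive, because its availability depends on surgery and on an effusion arising after randomisation. With one inferential time, no Hochberg step over time is needed here. State how patients without a Visit 2 or Visit 3 aspirate are handled, and report their number by group.
- **Visit 3.** Reconcile section 7.1.1 with sections 7.3.1 and 7.3.2 on who is aspirated.
- **Serum and urine.** Compare at Visits 2, 3, 5 and 6, with the Hochberg family defined over these four post-dose times. Say whether there is one family per marker and fluid.
- **Power.** State that the 1-year comparison applies to serum and urine only.
- **Test and groups.** Replace three groups with two, and the paired signed-rank test with a two-sample rank test.
- **2-week time.** Delete it or reconcile it with the visit schedule.

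The cost is a text amendment with IRB review (section 13.2) and no new samples. If the 2-week time is meant to stay, the schedule is affected as well and the cost is more than wording.
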